a significantly better neurologic outcome¹ and an uncontrolled case series, showed that steroid treatment reduced vessel wall enhancement.¹⁰ In contrast, it has also been postulated that infectious mechanisms may play a role in the pathophysiology of FCA-i, and concerns have been raised about possible adverse effects of steroid treatment on these mechanisms.^{11,12} The mechanism has best been studied for varicella related FCA-i: After systematic infection varicella virus remains in ganglions (“sleeping”). By reactivation there is a neuronal transport of the virus, followed by inflammatory process in the vessel wall.¹³ For other disease-causing microorganisms, the pathophysiology is less clear, but likely similar. Reflective of the resulting uncertainty and equipoise, a Delphi survey of pediatric stroke specialists identified a steroid trial in children with FCA-i as the most important and feasible trial in this research field.⁴

To assess the severity of stenosis and the course of FCA-i in a standardized manner, the Focal Cerebral Arteriopathy Severity Score (FCASS) was developed in 2018. It is calculated based on the degree of arterial stenosis in MR, CT or conventional angiography in five cerebral arterial segments. Consistent with the natural history of FCA-i, FCASS increases in the first months of the disease and then decreases thereafter. The score was shown to be reliable and to correlate with long-term outcome as well as stroke volume.^{12,14}

The objectives of this study are to evaluate if early anti-inflammatory treatment may influence

PASTA (Pediatric Arteriopathy Steroid Aspirin) trial

pediatric stroke

Study Protocol

the course of arteriopathy, improve clinical outcomes, and prevent stroke recurrence in children with FCA-i.

The primary hypothesis is, that children with FCA-i treated with a course of high dose methylprednisolone/prednisolone will show greater improvement of focal stenosis and arteriopathy as measured by FCASS.

Methods

Design

This is a PROBE-study, comparing a high-dose course of intravenous methylprednisolone/oral prednisolone plus standard care versus standard care alone in children with FCA-i. The study will be conducted in 27 centers in Australia, Austria, France, Germany, Switzerland, and the United Kingdom.

Recruitment of participants is planned to occur over a period of 36 months. The data collection is shown in Fig. 2.

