
● Functional impairment outcome by PSOM at 1, 3, 6 and 12 months● Recovery by RRQ at 1, 3, 6, and 12 months● Degree of disability or dependence by mRS at 1, 3, 6, and 12 months● Adaptive function by VABS at 6 and 12 months● For children aged >2 years, quality of life at 12 months, by PSQLM● Neurocognitive outcome at 12 months
Mixed clinical/imaging

● Stroke recurrence assessed at 1, 6 and 12 months defined as:
- New focal neurological deficit(s) or- Worsening of the neurological deficits by > 4 pedNIHSS points lasting for more than 24 hours with new or increased diffusion restriction in the corresponding vascular territory, or- New areas of clinically silent infarction, remote from the initial infarct
Safety Outcomes

● Late diagnosis of progressive large to medium vessel childhood primary angiitis of the CNS● Adverse events (abnormal blood pressure, abnormal blood glucose, behavioral problems, infections, gastrointestinal irritation, electrolyte abnormalities requiring

PASTA (Pediatric Arteriopathy Steroid Aspirin) trial

intervention or weight gain)

- Infectious episodes requiring hospitalization
- Serious adverse events related to the study intervention requiring medical intervention

Table 2: Outcome Measures. FCASS: Focal cerebral arteriopathy severity score; ASPECTS: Alberta stroke program early CT score, PSOM: Pediatric Stroke Outcome Measure; RRQ: Recurrence and Recovery Questionnaire; mRS: modified Rankin Scale; VABS: Vineland Adaptive Behavior Scale; PSQLM: Pediatric Stroke Quality of Life Measure; ped NIHSS: pediatric National Institute of Health Stroke Scale.

Imaging Outcomes

Magnetic resonance imaging and angiography (MRI/MRA) will be performed at baseline, 1 and 6 months and, if clinically indicated at 3 months. The imaging protocol will comprise at least DWI/ADC, FLAIR, T2-weighted, time of flight (ToF) MR angiography and SWI sequences. At baseline neck vessel and vessel wall imaging should be considered. MRIs should be performed at 3 Tesla and without sedation or anesthesia if possible. All images will be assessed centrally by two independent neuroradiologists.

The degree of arterial stenosis at different time points is measured using FCASS in MRA.

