Stroke Volume is measured by modified pediatric ASPECTS, a semi quantitative imaging score in childhood stroke where each abnormal area is assigned one point. Higher scores represent greater volumes, with a maximum possible score of 30 (15 per hemisphere).^{15,16}

Clinical Outcomes

PASTA (Pediatric Arteriopathy Steroid Aspirin) trial

pediatric stroke

Study Protocol

The pedNIHSS, an adaptation of the adult NIHSS to the pediatric population, is used to assess the severity of stroke.¹⁷ The Pediatric Stroke Outcome Measure (PSOM), which is used to determine neurologic outcome, was developed, and validated specifically for pediatric stroke. It addresses pediatric specific domains such as development, behavior and cognition in addition to sensory-motor and language function.^{18,19} To improve quality of data for pedNIHSS and PSOM, explanatory videos were created for all investigators. These are available at (<https://www.pasta-trial.ch>).

By telephone, the modified Rankin Scale (mRS) is collected to determine disability or dependence and the Recurrence and Recovery Questionnaire (RRQ) to determine recovery and recurrence. In addition, the Vineland adaptive behavior scale (VABS) is collected to monitor behavior and cognitive abilities. The VABS and mRS are widely used tests, which are well validated.^{20,21} The RRQ was specifically developed and validated for pediatric stroke patients and addresses pediatric- specific problems of manifestation of stroke and also difficulties in reliable clinical examination.²²

At the end of follow-up, Quality of life is assessed using the Pediatric Stroke Quality of Life Measure (PSQLM)²³ and standardized neurocognitive testing (using either WISC-V or WPPSI-IV, depending on age) is performed. Within the framework of this examination, children over the

PASTA (Pediatric Arteriopathy Steroid Aspirin) trial

pediatric stroke

Study Protocol

age of 8 are additionally assessed for executive functions using subtests of the Delis-Kaplan Executive Function System (D-KEFS) and attention using Continuous performance task (CPT-III).

Data monitoring body

On site monitoring will be conducted at the first 5 sites that enroll a participant as soon as their first participant has reached the 30-day follow-up visit. Subsequent on-site and remote monitoring visits will be done randomly and by risk-based assessment.

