Central data monitoring and validation will be performed according to a separate monitoring plan continuously for each site. This will include regular verification of the completeness, accuracy, and plausibility of the entered data and to query the site and follow up anything requiring clarification. No interim analyses are planned and no safety stopping points are defined.

Sample size estimates

For 13 patients of a retrospective study the standard deviation of the change in FCASS from baseline to maximum severity of arteriopathy was 2.8.¹⁴ Based on this standard deviation and a two-sample means test, 64 patients (32 in each group) are required to detect a difference of 2.0 with a power of 80% at a two-sided alpha-level of 0.05.

PASTA (Pediatric Arteriopathy Steroid Aspirin) trial

pediatric stroke

Study Protocol

To account for dropouts (8%), we will enlarge the sample size to 70 patients (35 in each group).

Statistical Analyses

The primary analysis will follow the intention-to-treat (ITT) principle. The primary outcome and secondary continuous variable outcomes that are measured multiple times during follow-up will be assessed in a repeated-measure, mixed-effects linear model.

Neurocognitive outcomes measured at 1 year will be analyzed using a mixed-effects linear model, binary outcomes (recovery, residual arteriopathy) will be assessed using generalized linear mixed-effects models, Time-to-event outcomes (stroke recurrence, infection requiring hospitalization, progressive arteriopathy) will be analyzed using Cox-regression, accounting for the stratification factors used at randomization (country and baseline FCASS).

We will perform a subgroup analysis according to baseline FCASS (<8 vs ≥8), accompanied by an appropriate test of interaction. Moreover, we will test whether the baseline FCASS (used continuously) has an influence on the association between steroid treatment and modified ASPECT score, i.e. whether there is effect modification (interaction).

Scores measured repeatedly over time (FCASS, mRS, PSOM, VABS, modified pediatric ASPECT) might be considered as categories. Patients may shift from category to category several times

PASTA (Pediatric Arteriopathy Steroid Aspirin) trial

pediatric stroke

Study Protocol

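### Stroke recurrence counts silent infarction up to 12 months, but no MRI is scheduled after 6 months, so that component has no planned ascertainment in months 6 to 12

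*Protocol*

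**What the plan says.** - **Outcome (Protocol, Table 2, Mixed clinical/imaging).** "Stroke recurrence assessed at 1, 6 and 12 months defined as" introduces three alternatives joined by *or*. One rests on imaging alone: "New areas of clinically silent infarction, remote from the initial infarct". The other two are clinical: a new focal deficit, and a worsening on the pedNIHSS "lasting for more than 24 hours with new or increased diffusion restriction in the corresponding vascular territory".
- **Scans (Protocol, Imaging Outcomes).** MRI/MRA "will be performed at baseline, 1 and 6 months and, if clinically indicated at 3 months". No 12-month scan is named, and the imaging outcomes in Table 2 also end at 6 months.
- **Clinical sources at 12 months (Protocol, Table 2 and Clinical Outcomes).** The telephone interview uses "the Recurrence and Recovery Questionnaire (RRQ) to determine recovery and recurrence", on the schedule "Recovery by RRQ at 1, 3, 6, and 12 months". PSOM, mRS, VABS, quality of life and neurocognition are also measured at 12 months.
- **Blinding (Protocol, Randomization and blinding).** Participants and local data collectors are unblinded. Images are read centrally and blinded, and the telephone interviews are central and blinded.
- **Analysis (Protocol, Statistical Analyses).** "Time-to-event outcomes (stroke recurrence, infection requiring hospitalization, progressive arteriopathy) will be analyzed using Cox-regression". No rule for dating events found on a scan is given.

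**The concern.** A clinically silent infarct has no sign that a visit, a questionnaire or a neurocognitive test could pick up. If the outcome runs to 12 months and the last planned scan is at 6, the same label covers two different outcomes: clinical plus silent events up to month 6, and in effect clinical events only afterwards. A reader of a 12-month recurrence result would assume uniform ascertainment.

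An analysis plan cannot repair this, because it cannot recover lesions that were never imaged. The definition and the scan schedule are both protocol content.

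There is also a route to bias. A scan after month 6 happens only if someone orders it, and the people ordering it know the treatment arm. A silent lesion found on such a scan would meet the definition as written. Blinded central reading protects how an image is read, not who is scanned. Preventing stroke recurrence is among the trial's stated objectives (Protocol, Introduction and rationale), so the outcome will be looked at even though the trial is not sized for it.

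**Working it through.** **1. The plan's own figures.** The protocol gives no recurrence rate, hazard ratio or power, so there is nothing to reproduce on this point. Its one computed design figure is the sample size for change in FCASS. With a difference of 2.0 and an SD of 2.8, a two-sample t-test needs 31.76, so 32 per arm and 64 in all; 64 / 0.92 = 69.6, so 70. It reproduces, but has no bearing on recurrence.

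**2. Definition against schedule.**

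| | Months |
|---|---|
| Recurrence assessed (Table 2) | 1, 6, 12 |
| MRI scheduled (Imaging Outcomes) | 0, 1, 6 (3 if clinically indicated) |
| Recurrence assessment without a scheduled scan | 12 |

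The uncovered window is 12 − 6 = 6 months, half of follow-up time. Half of the time is not necessarily half of the events.

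**3. Share of silent events arising after the 6-month scan (illustration; all rates assumed).** With a constant hazard and 12-month silent-infarct risk p, the risk by month 6 is 1 − √(1 − p), and the share arising later is f = 1 − [1 − √(1 − p)] / p.

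| Assumed p | Risk by month 6 | f |
|---|---|---|
| 5% | 2.53% | 49% |
| 10% | 5.13% | 49% |
| 20% | 10.56% | 47% |
| 30% | 16.33% | 46% |

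If instead 80–90% of silent events arise by month 6, f is 10–20%.

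**4. What unequal later scanning could do (illustration).** Suppose there is no treatment effect, all silent events up to month 6 are found, and a fraction s of later ones is found through unscheduled scans. The ratio of detected silent events between arms A and B is (1 − f + s_A·f) / (1 − f + s_B·f).

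| f | s = 10% vs 50% | s = 20% vs 40% |
|---|---|---|
| 0.456 | 0.590 / 0.772 = 0.76 | 0.635 / 0.726 = 0.87 |
| 0.20 | 0.82 / 0.90 = 0.91 | 0.84 / 0.88 = 0.95 |
| 0.10 | 0.91 / 0.95 = 0.96 | 0.92 / 0.94 = 0.98 |

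With equal s the ratio is 1. The scan fractions are assumptions, and nothing in the protocol says they will differ. In the composite, clinical events would dilute these ratios.

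**5. Does dating events to the scan matter?** Cox models were simulated with 35 per arm, an assumed 12-month risk of 30%, and events up to month 6. Each of 500 replicates was kept if both arms had an event.

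| True HR | Replicates kept | Mean log HR, true times | Mean log HR, dated to 1- or 6-month scan | SD (both) |
|---|---|---|---|---|
| 0.5 | 481 | −0.667 | −0.666 | 0.75 |
| 1.0 | 497 | 0.014 | 0.015 | 0.65 |

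Adding a 3-month scan in 80% of one arm and 20% of the other, with no true effect, gave an average HR of about 1.01 to 1.02 in two separate runs. Event dating up to month 6 is therefore not where the problem lies.

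**The case against.** **What stands on the other side**

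- Only one of three criteria is affected, and only in months 6 to 12. New deficits can be captured to 12 months by visit and by the blinded interview, and worsening can be confirmed by symptom-prompted imaging.
- A cumulative 12-month figure would still contain the silent infarcts found at the 1- and 6-month scans.
- The protocol describes a monophasic arteriopathy that progresses over days to weeks, with FCASS rising in the first months and then falling. That makes mostly early risk plausible, although those statements concern the arteries and not silent infarcts.
- This is a secondary outcome in a trial sized on FCASS change.

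These points limit the size of the problem. They do not close the gap between the definition and the scan schedule.

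**Stronger readings that the document does not support**

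- *That scan-detected events enter the Cox model as exact times.* The protocol names Cox regression and says nothing about dating. Such rules commonly belong in the analysis plan, which was not available here. With the same schedule in both arms, the effect is negligible (working, step 5).
- *That discretionary 3-month scans bias the hazard ratio.* Even a strong imbalance left the HR close to 1. Such a scan mostly re-dates a lesion that the 6-month MRI would probably show anyway.
- *That the whole 12-month composite cannot be measured.* This is true only of the silent component after month 6.
- *That progressive arteriopathy in the Cox list is a further unmeasurable outcome.* Table 2 has no outcome of that name, but it may be shorthand for the listed safety outcome of a late diagnosis of progressive CNS angiitis. At most this is a labelling mismatch.

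One caveat: "The data collection is shown in Fig. 2", and that figure could not be seen. The MRI schedule in the text is nevertheless explicit.

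**Conclusion.** The point holds for the silent-infarct component. As written, recurrence is assessed to 12 months with a criterion that has no planned ascertainment after 6 months, so its meaning changes at month 6. Silent lesions counted later would depend on scans ordered by unblinded clinicians.

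The size cannot be fixed from the documents. Under the assumed patterns, about 10–20% of silent events would be missed if risk is mostly early, and 46–49% if the hazard is constant. Any distortion of the treatment comparison requires unequal scanning between arms after month 6, which is possible in an open-label trial but is not shown. The change should be made: it concerns a secondary outcome, leaves the primary outcome untouched, and is cheap.

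**What to change.** In Table 2 and Statistical Analyses, replace the single recurrence outcome with two:

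- **(a) Clinical recurrence to 12 months**, using the clinical criteria exactly as Table 2 defines them, analysed by Cox regression.
- **(b) Clinical or silent recurrence up to the scheduled 6-month MRI**, counting silent lesions only from the scheduled 1- and 6-month MRIs, analysed as a binary outcome by 6 months.

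Taking silent lesions from scheduled scans only removes the dependence on who is sent for extra imaging. It also makes the dating of silent events irrelevant, because (b) is binary and (a) contains none.

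Separately, align progressive arteriopathy in the Cox list with a named Table 2 outcome, or remove it.

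**Cost.** Wording in the protocol and the analysis plan, with no additional scans. The silent-infarct claim ends at 6 months, and (b) needs a stated rule for children without a 6-month MRI.

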³⁴Department of Neurology, The Royal Children's Hospital, Murdoch Children's Research Institute and the University of Melbourne, Victoria, Australia.

³⁵French Centre for Paediatric Stroke, Hôpital Bellevue CHU Saint-Étienne, France

*Listed in Appendix 1

Corresponding author

[name]

[contact]

Running Title: PASTA Study Protocol

Key Words: Treatment, Pediatric Stroke, Focal Cerebral Arteriopathy, Steroid, Randomized Controlled Trial, FCA, Methylprednisolone, Protocol, PASTA

PASTA (Pediatric Arteriopathy Steroid Aspirin) trial

Pediatr Stroke. 2023;6: 21-42

www.pediatricstrokejournal.com

pediatric stroke

Study Protocol

Abstract

Rationale

Focal cerebral arteriopathy (FCA), a unilateral, monophasic disease of the intracranial arteries, is one of the most common etiologies of pediatric stroke. Imaging and laboratory evidence suggest an underlying inflammatory mechanism. The arteriopathy can progress over days to weeks, conferring a high risk of additional ischemic brain injury. Given its presumed inflammatory origin, there has been recently an emerging trend to intervene with corticosteroid treatment. However, there is a paucity of evidence on whether steroid treatment improves outcomes.

Aim

The aim of this study is to investigate whether high dose corticosteroids result in greater and faster improvement of focal stenosis in children with stroke and FCA and how this intervention influences neurological and neuropsychological outcomes as well as quality of life.

Sample size estimates

A sample size of 64 patients assigned 1:1 to the two study arms is required to detect a clinically relevant difference of 2.0 in the primary outcome with a power of 80% at a two-sided

PASTA (Pediatric Arteriopathy Steroid Aspirin) trial

Pediatr Stroke. 2023;6: 21-42

www.pediatricstrokejournal.com

pediatric stroke

Study Protocol

alpha-level of 0.05.

Methods and design

This is a Prospective Randomized Open, Blinded Endpoint (PROBE) study involving 27 centers in Europe and Australia. Patients between 6 months and 18 years with a unilateral arteriopathy will be enrolled during a recruitment period of 3 years. A total of 70 participants (accounting for 8% dropouts) will be centrally randomized to standard care (including aspirin) alone or standard care plus high-dose-corticosteroids (experimental arm) in a ratio 1:1.

Study outcomes

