At the time of this publication the study protocol was approved by all corresponding regulatory authorities and the local ethic committees in Switzerland (BASEC-ID: 2021-00453), Austria (EK Nr: 2136/2021), France (N° de dossier: 21.04056.000061–22014), Germany (Aktenzeichen:

PASTA (Pediatric Arteriopathy Steroid Aspirin) trial

pediatric stroke

Study Protocol

2022-066-f-A) as well as UK (IRAS ID: 305395) and Australia (RCH HREC Reference Number: 78937). The study is registered at ClinicalTrials.gov (NCT04873583).

Patient population

All patients older than 6 months and younger than 18 years with unilateral FCA-i will be screened on admission. The complete eligibility criteria are provided in table 1.

Inclusion criteria	Exclusion criteria
1. Written informed consent (legal representative)	1. Previous stroke
2. Age 6 months to under 18 years	2. Genetic vasculopathies include ACTA2, neurofibromatosis type 1, trisomy 21
3. Randomization possible within 48 hours of diagnosis and maximum 96 hours after symptom onset	3. Moyamoya or sickle cell disease
4. Symptomatic unilateral cerebral arteriopathy (newly acquired neurological deficits of proven ischemia and unilateral stenosis/vessel irregularity on neuroimaging)	4. Craniocervical arterial dissection
5. Female participants age \geq 13: Negative pregnancy test	5. Primary (small vessel) and secondary angiitis of the CNS
	6. Bilateral arteriopathy
	7. Underlying systemic disorders e.g., rheumatological
	8. On steroid treatment at disease onset
	9. Contraindication to corticosteroid treatment
	10. Inability to follow study-procedures
	11. Participation in another interventional study

Table 1: Eligibility criteria

PASTA (Pediatric Arteriopathy Steroid Aspirin) trial

pediatric stroke

Study Protocol

The diagnosis of unilateral cerebral arteriopathy (inclusion criterion 4) will be made on site by the respective study team. If the diagnosis is not clear, the sponsor will be contacted to review the MRI images together with the neuroradiologists at the sponsor's site. Subsequently, the sponsor and study site will seek a joint agreement as to whether or not the patient fulfills the eligibility criteria.

Randomization and blinding

Allocation will be done in a 1:1 ratio of standard care alone (including aspirin) or standard care plus corticosteroids (See Fig. 3) using web-based randomization with secuTrial.

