Probabilistic minimization will be used, accounting for the following stratification factors: age (6 months through 5 years, 6 years through 11 years, 12 years to under 18 years) and pediatric National Institute of Health Stroke Scale (Ped-NIHSS; < 7, 7 to 12, >12).

Trial participants and local data collectors will not be blinded, as steroid treatment causes obvious clinical signs and symptoms. Imaging outcomes will be centrally assessed by blinded neuroradiologists.

The telephone-interview-based assessments of RRQ (Recurrence and Recovery Questionnaire), mRS (modified Rankin Scale) and VABS (Vineland Adaptive Behavior Scales) will be performed

PASTA (Pediatric Arteriopathy Steroid Aspirin) trial

pediatric stroke

Study Protocol

blinded centrally for all study participants.

Intervention

Participants in both study arms will be treated based on standard care, including antithrombotic treatment with daily oral aspirin (3-5mg/kg/day, maximum 150mg/day). The hyperacute treatment (including intravenous thrombolysis and endovascular thrombectomy) may be performed according to local protocol. Start with any type of anticoagulation is possible and should be done as by local protocol. Switch or start of aspirin is mandatory at latest at inclusion. Suggestions (see supplementary) for standard care are given to the sites but noncompliance is not a deviation to the protocol. These suggestions have been discussed and approved by the international steering committee of the PASTA trial (see Appendix 1).

In addition, participants in the treatment arm will receive 3 days of intravenous methylprednisolone 30mg/kg/day (max. 1000mg/dose) in one daily dose. This is followed by therapy with oral prednisolone 1 mg/kg/day (max. 40mg/day) for 2 weeks and 0.5mg/kg/day (max. 20mg/day) for another 2 weeks.

Outcomes

The Primary Outcome is the change in FCASS from baseline examination to 1 month. In

PASTA (Pediatric Arteriopathy Steroid Aspirin) trial

Pediatr Stroke. 2023;6: 21-42

www.pediatricstrokejournal.com

addition, various imaging data, clinical and safety outcomes will be assessed (see table 2).

Primary Outcome

● Change in FCASS from baseline to 1 month
Secondary Outcomes
Imaging

● Change in FCASS from baseline to 6 months● Volume of stroke (in FLAIR and DWI-sequences) at baseline, 1, 3 and 6 months by modified pediatric ASPECTS● Residual arteriopathy at 6 months by FCASS
Clinical

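### The only serious-adverse-event outcome is limited to intervention-related events, so it cannot be compared between the randomized arms

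*Protocol*

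**What the plan says.** In the protocol's Outcomes section, Table 2 lists four safety outcomes. The only one on serious adverse events reads "Serious adverse events related to the study intervention requiring medical intervention". It has two conditions: attribution to the intervention, and a need for medical treatment. No SAE outcome without these conditions is listed.

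The other three safety outcomes are a late diagnosis of progressive CNS angiitis, a list of adverse event types, and infections leading to hospital admission. None of them requires a causal link to treatment.

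The study intervention is not defined as a term. The Aim in the abstract is about high-dose corticosteroids and asks "how this intervention influences neurological and neuropsychological outcomes as well as quality of life". Randomization and blinding describes the allocation as "standard care alone (including aspirin) or standard care plus corticosteroids". The Intervention section covers aspirin for both arms ("Switch or start of aspirin is mandatory at latest at inclusion") and then adds the steroid course for one arm: "participants in the treatment arm will receive 3 days of intravenous methylprednisolone".

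On blinding, the protocol states: "Trial participants and local data collectors will not be blinded, as steroid treatment causes obvious clinical signs and symptoms". Imaging and the telephone interviews are assessed centrally and blinded. No such arrangement is described for SAE causality.

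**The concern.** A randomized comparison of harm needs an event that can be counted in the same way in both arms. This outcome makes counting depend on a link to a treatment that one arm does not receive. Two things follow.

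First, the count can only put the steroid arm level with or above the control arm. If steroids reduced serious events, this outcome could not show it.

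Second, a serious event in a steroid-treated child that is attributed to the underlying stroke drops out. This matters here because the Introduction reports concern that steroids might act adversely on infectious mechanisms of the disease. Harm of that kind could look like disease progression. The protocol also plans no interim analyses and sets no safety stopping points, so the end-of-trial safety outcomes carry more weight.

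The protocol fixes this definition itself, so it is not a detail left to a later analysis plan.

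**Working it through.** **Step 1. Who can contribute an event?**

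| Reading of the study intervention | Control arm | Steroid arm |
|---|---|---|
| Corticosteroid course (Aim, allocation wording) | No event possible if treated as allocated | Events judged related to steroids |
| Everything under the Intervention heading, including aspirin | Events judged related to aspirin | Events judged related to aspirin or to steroids |

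The first reading is the natural one: the Aim uses the word for corticosteroids, and aspirin is placed inside standard care. The second reading does not restore comparability, because one arm can be attributed events from one agent and the other arm from two.

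**Step 2. Number per arm.** The documents give no SAE rate. The only figure taken from them is the arm size, so I checked that it reproduces. Inputs from Sample size estimates: difference 2.0, SD 2.8, power 80%, two-sided alpha 0.05, dropout 8%.

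- Normal approximation: n = 2 × (1.96 + 0.842)² × 2.8² / 2.0² = 30.8, so 31 per arm.
- Two-sample t-test: 31.76, so 32 per arm and 64 in total, as stated (power 0.803).
- Dropout: 64 / 0.92 = 69.6, so 70, or 35 per arm, as stated.

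**Step 3. Illustration with assumed counts (steroid reading).**

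- Equal truth, 5/35 in each arm: the outcome reads 0/35 in controls and between 0/35 and 5/35 with steroids, depending only on attribution.
- Steroids halve SAEs, 3/35 against 6/35: the outcome reads up to 3/35 with steroids against 0/35 in controls, so the direction is reversed.

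**Step 4. Range over assumed rates.** Let p be the true SAE rate, equal in both arms, and let a be the share of steroid-arm SAEs judged related. The true difference is 0. The expected counts are 35 × p × a with steroids and 0 in controls, and the apparent risk difference is p × a.

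For scale only, suppose someone applied a two-sided Fisher exact test. With k events against none, p-value = 2 × C(35,k) / C(70,k). This gives 0.054 for k = 5 and 0.025 for k = 6, so six events suffice. The last column is the binomial probability of six or more events among 35 at rate p × a.

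| p (assumed) | a (assumed) | Expected steroid-arm count | Apparent risk difference | Chance of 6 or more |
|---|---|---|---|---|
| 5% | 25% | 0.44 | 1.25 points | below 0.1% |
| 10% | 50% | 1.75 | 5 points | 0.7% |
| 20% | 50% | 3.5 | 10 points | 13% |
| 30% | 50% | 5.25 | 15 points | 43% |
| 20% | 100% | 7.0 | 20 points | 73% |
| 30% | 100% | 10.5 | 30 points | 97% |

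The size depends heavily on p and a, and neither is in the documents. The direction depends on neither. If SAEs were counted regardless of attribution, the expected difference would be 0 in every row.

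**The case against.** Several stronger readings are tempting, and the protocol does not support them.

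- **That a biased comparison is planned.** No between-arm SAE analysis is specified. Statistical Analyses assigns Cox regression to infection requiring admission, stroke recurrence and progressive arteriopathy, but not to SAEs. The abstract speaks only of analysing adverse reactions, which fits a descriptive listing. This stands: the fault lies in what the outcome can be used for, and the Fisher figures above describe a test the protocol does not propose.
- **That control events are impossible by definition.** This is too strong. The term is undefined, mandatory aspirin sits under the Intervention heading, and a control child given steroids off-protocol would stay in the control arm under intention to treat.
- **That this is the main safety measure and randomized safety evidence is lost.** Table 2 does not rank its safety outcomes, and the other three can be counted in both arms. Neurological worsening with new or increased diffusion restriction is captured under stroke recurrence, with no relatedness filter.
- **That unblinded site staff decide causality.** Local data collectors are unblinded, but the protocol does not say who attributes SAEs or whether attribution is reviewed centrally. What can be said is that no blinded assessment is described.
- **That no table of all SAEs will exist.** The statistical analysis plan is not at hand and may contain one.

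These points narrow the concern without removing it. None supplies an all-cause SAE outcome in Table 2. A death or bleed outside the listed event types and the recurrence definition counts as a safety outcome only if it is judged related.

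**Conclusion.** The point holds in a limited form. The single SAE outcome depends on attribution to a treatment that, on the natural reading, only one arm receives. It should not be read as a between-arm comparison: it cannot show a reduction in SAEs with steroids, and it can leave out harm attributed to the disease.

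This conclusion rests on reading the study intervention as the corticosteroid course and on controls being treated as allocated. Under the wider reading that includes aspirin, the arms still differ in what can be attributed.

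The size cannot be taken from the documents. Over assumed SAE rates of 5% to 30% and assumed attribution shares of 25% to 100%, equal true risk would appear as an excess of 1.25 to 30 percentage points in the steroid arm. The primary outcome, the sample size, the other safety outcomes and stroke recurrence are unaffected. The change should be made, but it is confined to one line of Table 2 and one missing definition.

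**What to change.** Replace the SAE line in Table 2 with: *children with at least one serious adverse event, regardless of relatedness, from randomization to 12 months, by randomized arm, with risk difference and 95% confidence interval*. The 12 months match the last clinical follow-up in Table 2.

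Keep related SAEs as a descriptive listing, and define the study intervention, stating whether aspirin is included.

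The cost is protocol wording, matching text in the analysis plan and slightly more tabulation, provided that all SAEs are already collected in both arms. The protocol text at hand does not confirm this, so it should be checked first. The downside is that the new count will include more events caused by the stroke itself. That is acceptable, because randomization balances such events in expectation and the listing of related events remains.
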